4.2.5.1.2 Viral Resistance Measurements

Resistance-associated variants of the HCV can lead to failure of therapy. This is one of the most important considerations when treating with a DAA. To better understand and document the potential for RAVs to impact treatment with MK-3682 + RZR, blood samples for viral resistance assays will be collected at Baseline (Day 1) to determine pre-existing RAVs to MK-3682 and RZR. Next-generation sequencing will be performed with a 15% sensitivity threshold. Additional resistance testing on these samples may be performed. Blood samples for resistance testing are also collected during the follow-up period, as well as at the virologic failure confirmation visit (should this occur) for genotypic and investigational assays to assess emergence of resistance to MK-3682 and/or RZR following treatment initiation. Resistance-associated variants will be assessed for any subject who has detectable virus above 1000 IU/mL and has met a virologic failure criteria. Subjects who fail due to early discontinuation of study medication and continue in the trial may also have samples collected and tested for RAVs at each follow-up visit, if the virus is detectable and $>$ 1000 IU/mL.

4.2.5.2 Safety Endpoints

The safety and tolerability of the study regimen will be assessed by a clinical evaluation of AEs and inspection of other study parameters including vital signs, physical examinations, 12-lead ECGs, and standard laboratory safety tests at appropriate time points as specified in the Trial Flow Chart (Section 6.0). Adverse events are graded and recorded according to Section 7.2. Subjects may be asked to return for unscheduled visits in order to perform additional safety monitoring.

4.2.5.3 Pharmacokinetic Endpoints

The primary PK endpoints for MK-3682 (and metabolites) and RZR are trough plasma concentration (C_{trough}). PK samples will be collected from all subjects on each visit as described in the Trial Flow Chart (Section 6) and in Table 13 (Pharmacokinetic and Pharmacodynamic Sampling Time Points). These samples will be used to evaluate PK concentrations, and PK/AE relationships of MK-3682 (and metabolites) and RZR, as appropriate. The predose time points outlined were chosen in order to capture C_{trough} for all compounds. The frequency of C_{trough} collections will allow a thorough assessment of both subject drug concentrations and drug compliance, should a breakthrough occur. In addition, the postdose time points, in conjunction with the other samples, will be used for PK-safety and PK-efficacy modeling.

4.2.5.4 Pharmacodynamic Endpoints

As described in Section 7.1.3.2, a subgroup of the study population will be included in an intensive viral kinetic sub-study. The purpose of this sub-study is to determine whether early viral kinetics can aid in developing a PK/PD model that can predict combinations that may be efficacious with various treatment durations.

These subjects will have HCV RNA samples collected during Week 1 as described in the Trial Flow Chart (Section 6.0) and in Table 13 (Pharmacokinetic and Pharmacodynamic Sampling Time Points). In addition, PK samples will also be collected as described in Table 13. These samples will be used to evaluate the PK/PD relationships of MK-3682 (and metabolites) and RZR, as appropriate.

4.2.5.5 Planned Exploratory Biomarker Research

Planned Genetic Analysis

Understanding genetic determinants of drug response and the molecular basis of disease is an important endeavor during medical research. This research will evaluate whether genetic variation within a clinical trial population correlates with response to the treatment(s) under evaluation and/or disease. If genetic variation is found to predict efficacy or adverse events, the data might inform optimal use of therapies in the patient population. Knowledge of the molecular basis of disease contributes to the development of novel biomarkers and the identification of new drug targets. This research contributes to understanding molecular basis of disease and the genetic determinants of efficacy and safety associated with the treatments in this study.

In addition to studying variation across the human genome, for example, IL28B genetic variants will specifically be investigated for understanding variation in clinical endpoints for example, but not limited to, SVR and other efficacy and safety measurements.

4.2.5.6 Future Biomedical Research

The Sponsor will conduct Future Biomedical Research on specimens consented for future biomedical research during this clinical trial. This research may include genetic analyses (DNA), gene expression profiling (RNA), proteomics, metabolomics (serum, plasma) and/or the measurement of other analytes, depending on which specimens are consented for future biomedical research.

Such research is for biomarker testing to address emergent questions not described elsewhere in the protocol (as part of the main trial) and will only be conducted on specimens from appropriately consented subjects. The objective of collecting/retaining specimens for Future Biomedical Research is to explore and identify biomarkers that inform the scientific understanding of diseases and/or their therapeutic treatments. The overarching goal is to use such information to develop safer, more effective drugs/vaccines, and/or to ensure that subjects receive the correct dose of the correct drug/vaccine at the correct time. The details of this Future Biomedical Research sub-trial are presented in Section 12.2 – Collection and Management of Specimens for Future Biomedical Research.

4.3 Benefit/Risk

Subjects in clinical trials generally cannot expect to receive direct benefit from treatment during participation, as clinical trials are designed to provide information about the safety and effectiveness of an investigational medicine.

There remains a critical need for new HCV therapies. The treatment regimen combining an HCV NS5B NI (MK-3682), and an NS5A complex inhibitor (RZR), has the potential to provide efficacy across multiple GTs and across diverse patient populations, and improve treatment by eliminating the need for RBV and shortening the duration of therapy. The improved potency against RAVs observed with earlier generation NS5A inhibitors suggests that MK-3682 in combination with RZR may provide a stronger barrier to the development of resistance and increased activity in the setting of baseline resistance variants.

MK-3682

MK-3682 is a potent HCV NS5B NI with pangenotypic activity and a high barrier to resistance that, in combination with complementary HCV DAAs, has the potential to benefit an expanded spectrum of HCV-infected subjects, including those with currently difficult-to-treat GTs of HCV and individuals who have failed previous treatments. Among all the known DAA classes, NIs have displayed the broadest HCV genotypic coverage and the highest barrier to the development of resistance.

MK-3682 belongs to a class of uridine-based nucleotide analogs, e.g., SOF, that have been generally well tolerated. However, there have been postmarketing reports of symptomatic bradycardia, including one fatal cardiac arrest and cases requiring pacemaker insertion, in subjects taking the antiarrhythmic drug amiodarone together with either LDV/SOF or SOF in combination with another DAA.

The toxicity potential of MK-3682 has been well characterized in *in vitro* mitochondrial toxicity assays, a battery of *in vitro* and *in vivo* genetic toxicity studies, safety pharmacology studies, and 4-week, 3-month and 6-month repeat-dose oral toxicity studies in rats and monkeys. *In vitro* and *in vivo* preclinical data demonstrate that MK-3682 and its metabolite, M6, at the exposures observed in the clinic, have limited potential for class toxicities associated with nucleotides, including myopathy and mitochondrial toxicity. No observed adverse effect levels (NOAELs) in the rat and Cynomolgus monkey at 1000 mg/kg/day provide adequate margins of safety relative to anticipated human doses and support daily oral dosing of humans for up to 6 months in duration. In summary, the toxicity studies identified minimal differences between control and treated animals, all of which were not considered adverse. Preclinical studies identified the liver and potentially kidney as potential target organs. There was no evidence of cardiovascular toxicity in studies up to 3 months' duration, based on histopathology in the rat and monkey and echocardiography, electrocardiography, and serum biomarker evaluations in the monkey. Overall, the preclinical toxicity profile of MK-3682 via the oral route of administration supports the continuation of clinical trials.

To date, MK-3682 has been generally well-tolerated in healthy subjects and HCV-infected subjects in several Phase 1 clinical studies at single doses up to 900 mg, multiple doses up to

750 mg per day for 10 days, and in Phase 2a trials of 300 mg or 450 mg once daily for up to 24 weeks. Review of the safety data has revealed no clinically significant abnormalities in routine physical examinations including vital signs. There have been no dose-related or other patterns observed in the clinical, ECG, or laboratory data. In the clinical studies proposed, available safety data (clinical and laboratory AEs, vital signs, laboratory safety tests, and ECGs) will be carefully monitored.

Phase 2 studies have demonstrated that a regimen of MK-3682 (450 mg)/GZR/RZR is highly effective in GT1, 2, and 3-infected subjects. Overall, MK-3682, as a component of a combination DAA regimen, has the potential to substantially improve HCV treatment outcomes, benefiting many HCV-infected individuals.

RZR

RZR is a potent HCV NS5A complex inhibitor with pangenotypic activity that has the potential to benefit individuals requiring treatment of HCV infection, even if the individual is infected with currently difficult-to-treat GTs. The improved potency of RZR against RAVs observed with earlier generation NS5A inhibitors suggests that RZR will have improved efficacy in individuals who have experienced treatment failures with other anti-HCV regimens and/or have NS5A RAVs at baseline.

RZR has favorable safety findings in safety assessment toxicity studies and ancillary pharmacology studies, supporting the continued evaluation of RZR in clinical trials in adults. The 2-week, 3-month, 6-month, and 9-month rat and dog toxicity studies provide substantial preclinical safety margins for doses proposed to be administered in future clinical trials. RZR has been given to approximately 217 subjects and subjects in 8 RZR Phase 1 trials and in over 800 subjects in ongoing Phase 2a trials (RZR in combination with MK-3682 and GZR in HCV GT1-, GT2-, and GT3-infected subjects). RZR has been administered at doses up to 600 mg/day, 100 mg given daily for 10 days, and 60 mg once daily for up to 24 weeks. No SAEs have been reported in any individual receiving RZR. There were no consistent treatment-related changes in labs, vital signs, or ECG safety parameter values. Adverse events in subjects receiving RZR monotherapy have been mild to moderate in intensity and transient in duration. The totality of the safety data indicates that RZR is well-tolerated.

Definitive embryo-fetal developmental toxicity studies conducted in concordance with the International Conference on Harmonization (ICH) of Technical Requirements for Registration of Pharmaceuticals for Human Use M3 (R2) guidance have been completed in rats and rabbits for MK-3682 and RZR. While data support the inclusion of women of childbearing potential in clinical trials with MK-3682 and RZR, inclusion of women of childbearing potential should be in accordance with the study protocol and applicable regulatory guidance.

Based on the preclinical data and the clinical experience to date in healthy subjects and HCV-infected subjects, the risk/benefit assessment is favorable for proceeding with the proposed clinical study with the 2-drug combination of MK-3682 + RZR.

Additional details regarding specific benefits and risks for subjects participating in this clinical trial may be found in the accompanying IB and Informed Consent documents.

5.0 METHODOLOGY

5.1 Entry Criteria

5.1.1 Diagnosis/Condition for Entry into the Trial

Male/Female subjects with chronic HCV GT1, GT2, GT3, GT4, GT5, or GT6 infection who are at least 18 years of age will be enrolled in this trial.

5.1.2 Subject Inclusion Criteria

In order to be eligible for participation in this trial, the subject must:

1. be ≥ 18 years of age on day of signing informed consent
2. have HCV RNA ($\geq 10,000$ IU/mL in peripheral blood) at the time of screening
3. have documented chronic HCV GT1, GT2, GT3, GT4, GT5, or GT6 (with no evidence of non-typeable or mixed GT) infection as follows:
 - a. positive for anti-HCV antibody, HCV RNA, or HCV GT1, GT2, GT3, GT4, GT5, or GT6 at least 6 months before Day 1, **or**
 - b. positive for anti-HCV antibody or HCV RNA with a liver biopsy consistent with chronic HCV infection (such as the presence of fibrosis) before Day 1
4. have liver disease staging assessment as follows:
 - a. **Absence of cirrhosis (F0 to F3) defined as any one of the following:**
 - i. a liver biopsy performed within 24 months of Day 1 of this study showing absence of cirrhosis
 - ii. Fibroscan[®] performed within 12 months of Day 1 of this study with a result of ≤ 12.5 kPa, **or**
 - iii. a Fibrosure[®] (Fibrotest[®]) performed during screening with a score of ≤ 0.48 **and** an aspartate aminotransferase (AST) to platelet ratio index (APRI) of ≤ 1
 - b. **Compensated cirrhosis (F4) defined as any one of the following:**
 - i. a liver biopsy performed prior to Day 1 of this study showing cirrhosis
 - ii. Fibroscan[®] performed within 12 months of Day 1 of this study showing cirrhosis with result > 12.5 kPa, **or**
 - iii. a Fibrosure[®] (Fibrotest[®]) performed during screening with a score of > 0.75 **and** an APRI of > 2

APRI formula: $AST \div lab\ ULN\ for\ AST \times 100 \div (platelet\ count \div 100)$. APRI calculation to be provided by the testing laboratory.

NOTE: In the absence of a definitive diagnosis of presence or absence of cirrhosis by the above criteria, a liver biopsy or Fibroscan[®] is required. Liver biopsy results supersede the results obtained by Fibroscan[®] or Fibrosure[®].

5. have an HCV treatment status that is one of the following:
 - a. HCV treatment naïve (defined as no prior exposure to any IFN-containing regimen, RBV, or other approved or experimental HCV-specific DAA agent).
 - b. HCV treatment experienced (defined as prior virologic failure after treatment with an IFN-containing regimen, with or without RBV, or intolerance to an IFN-containing regimen). Subjects cannot have previously received treatment with HCV-specific DAA agent.
6. meet one of the following categories:
 - a) The subject is a male who is not of reproductive potential, defined as a male who has azoospermia (whether due to having had a vasectomy or due to an underlying medical condition).
 - b) The subject is a female who is not of reproductive potential, defined as a female who either: (1) is postmenopausal (defined as at least 12 months with no menses in women ≥ 45 years of age); (2) has had a hysterectomy and/or bilateral oophorectomy, bilateral salpingectomy, or bilateral tubal ligation/occlusion at least 6 weeks prior to screening; OR (3) has a congenital or acquired condition that prevents childbearing.
 - c) The subject is a female or a male who is of reproductive potential and agrees to avoid becoming pregnant or impregnating a partner beginning at least 2 weeks prior to administration of the initial dose of study drug, and for **6 months after taking the last dose** of study drug (or longer if dictated by local regulations) by complying with 1 of the following: (1) practice abstinence[†] from heterosexual activity OR (2) use (or have their partner use) **2** forms of acceptable contraception during heterosexual activity. Acceptable methods of contraception are as follows[‡]:
 - intrauterine device (with or without local hormone release)
 - diaphragm with spermicide (cannot be used in conjunction with cervical cap/spermicide)
 - cervical cap with spermicide (nulliparous women only)
 - contraceptive sponge (nulliparous women only)
 - male condom with spermicide or female condom with spermicide (cannot be used together)
 - hormonal contraceptive: oral contraceptive pill (estrogen/progestin pill or progestin-only pill), contraceptive skin patch, vaginal contraceptive ring, or subcutaneous contraceptive injection

If male, subjects must agree to use a condom with spermicide or abstain from sexual intercourse during the trial until **6 months after taking the last dose** of study drug (or longer if dictated by local regulations).

Spermicides alone are not an acceptable method of contraception.

Subjects must be completely informed of the unknown risks of pregnancy and agree not to become pregnant during the time they are participating in this trial.

If there is any question that a subject will not be reliable in the use of appropriate contraceptive methods, they should not be entered into the trial.

NOTE: Subjects whose study medication regimen includes only MK-3682 + RZR (and are not treated at any time with RBV) should avoid becoming pregnant or impregnating a partner for at least **14 days after taking the last dose** of study drug. Acceptable methods of contraception for these subjects during this time include:

Single method (one of the following is acceptable):

- intrauterine device (IUD)
- vasectomy of a female subject's male partner
- contraceptive rod implanted into the skin

Combination method (requires use of two of the following):

- diaphragm with spermicide (cannot be used in conjunction with cervical cap/spermicide)
- cervical cap with spermicide (nulliparous women only)
- contraceptive sponge (nulliparous women only)
- male condom or female condom (cannot be used together)
- hormonal contraceptive: oral contraceptive pill (estrogen/progestin pill or progestin-only pill), contraceptive skin patch, vaginal contraceptive ring, or subcutaneous contraceptive injection

†Abstinence (relative to heterosexual activity) can be used as the sole method of contraception if it is consistently employed as the subject's preferred and usual lifestyle and if considered acceptable by local regulatory agencies and ERCs/IRBs. Periodic abstinence (e.g., calendar, ovulation, sympto-thermal, post-ovulation methods, etc.) and withdrawal are not acceptable methods of contraception.

‡If a contraceptive method listed above is restricted by local regulations/guidelines, then it does not qualify as an acceptable method of contraception for subjects participating at sites in this country/region.

7. understand the study procedures, alternative treatments available, risks involved with the study, and voluntarily agrees to participate by giving written informed consent. The subject may also provide consent for FBR. However, the subject may participate in the main trial without participating in FBR.

For HIV co-infected subjects, these additional 2 criteria must also be met:

8. have HIV-1/HIV-2 infection documented at any time prior to study entry (Day 1) by any licensed rapid HIV test or HIV enzyme or chemiluminescence immunoassay (E/CIA) test kit and confirmed by a licensed Western blot or a second antibody test by a method other than the initial rapid HIV and/or E/CIA, or by HIV-1 p24 antigen, or plasma HIV-1 RNA VL.
9. meet 1 of the following criteria:
 - a. not currently on antiretroviral therapy (ART) and has no plans to initiate ART treatment while participating in this study, must have CD4+ T-cell count >500 cells/mm³ at time of screening, or
 - b. have well controlled HIV on ART, defined as the following:
 - i. must have CD4+ T-cell count >200 cells/mm³ at time of screening
 - ii. must have achieved and maintained virologic suppression (defined as confirmed HIV RNA level $<$ LLOQ of available assay) for at least 8 weeks prior to screening
 - iii. must have been on a stable regimen (without changes in drugs or dose modification) for at least 4 weeks prior to study entry (Day 1)

The combination ART regimen must not contain any antiretroviral medications other than: abacavir, dolutegravir, emtricitabine, lamivudine, raltegravir, rilpivirine or tenofovir.

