- f. Any major medical condition, clinically-significant illness (other than HCV), pre-study laboratory or ECG abnormality, or history of any illness, which, in the opinion of the investigator, might interfere with subject treatment, assessment, compliance with the protocol, or confound the results of the study or pose additional risk in administering the study drug to the subject.
- g. History of a medical/surgical condition that resulted in hospitalization within the 3 months prior to enrollment, other than for minor elective procedures.
NOTE: Elective procedures will be permitted following 14 days after taking the last dose of study drug.
- h. Medical/surgical conditions that may result in a need for hospitalization during the period of the study.
- i. Any medical condition requiring, or likely to require, chronic systemic administration of corticosteroids, tumor necrosis factor (TNF) antagonists, or other immunosuppressant drugs during the course of the trial through FW24.
- j. Life-threatening SAE during the screening period.
- k. Evidence of history of chronic hepatitis not caused by HCV, including but not limited to drug-induced hepatitis, hemochromatosis, Wilson's disease, α 1-antitrypsin deficiency, alcoholic liver disease, and autoimmune hepatitis (See Exclusion Criterion #4 regarding evidence of history of Hepatitis B).

NOTE: Subjects with history of acute non-HCV-related hepatitis, which resolved >6 months before study entry, can be enrolled.

13. has exclusionary laboratory values at the screening visit as listed in [Table 6](#).

NOTE: If any of the laboratory exclusion criteria in [Table 6](#) are met, the site may have the abnormal value retested 1 time.

Table 6 Laboratory Exclusion Criteria

Laboratory Assessment	Exclusionary Values
Creatinine Clearance (estimated glomerular filtration rate, eGFR) [†]	<50 mL/min/1.73 m ²
Hemoglobin	<10 g/dL
Platelets	<50 × 10 ³ /μL
Serum Albumin	<3.0 g/dL
International normalized ratio (INR)	>1.7 unless subject has a stable INR on an anticoagulant regimen
ALT	>10× ULN
AST	>10× ULN

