7.1.2.7 Noninvasive Methods of Cirrhosis Evaluation

FibroScan[®]: This method for assessing liver cirrhosis has gained increasing acceptance. In the US, this methodology is Food and Drug Administration (FDA) approved and, in other countries, it is often the preferred method of assessment. FibroScan[®] results are influenced by a number of confounders including ALT, ascites, and underlying disease. Hepatitis C is one of the best studied and is the disease state with the most reproducible/reliable results. FibroScan[®] has been evaluated in many liver diseases for the staging of liver fibrosis, and has been demonstrated to be very effective for differentiating cirrhosis (F4) from no cirrhosis (<F4), but it is less capable of differentiating gradations of fibrosis. In a large study by Castera, et al [40], a population of patients with chronic HCV infection, a cutoff of 12.5 kPa was selected for cirrhotics. At this cutoff, the sensitivity and specificity of the test for cirrhosis were 87% and 91%, respectively, and the negative predictive value was 95%. Since this analysis was assessed specifically in subjects with chronic HCV infection, the cutoff value >12.5 kPa used by Castera was selected to include cirrhotics in the current study.

FibroTest[®] + APRI: Various methodologies have been developed in order to improve the sensitivity and specificity of blood tests used to diagnose cirrhosis in patients with chronic HCV infection. One such algorithm, the sequential algorithm for fibrosis evaluation (SAFE), which uses a combination of FibroTest[®] and the APRI, is very accurate for diagnosing cirrhosis [41]. For cirrhosis, the SAFE for F4 algorithm provides a diagnostic accuracy of 89.5% with a negative predictive value of 94.6%. Using this algorithm, it is estimated that only 6.2% of the patients would need a liver biopsy to confirm the diagnosis of cirrhosis. The cutoff values for excluding cirrhotics using the 2 tests, without the use of liver biopsy, are ≤ 1 and ≤ 0.48 for FibroTest[®] and APRI when the SAFE for F4 is used. This study uses this method with one variation, which is the more stringent requirement that both the APRI and FibroTest[®] need to be consistent with no cirrhosis (i.e., APRI is ≤ 1 AND FibroTest[®] ≤ 0.48).

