8.10 Subgroup Analyses and Effects of Baseline Factors

The subgroup analyses detailed below will be performed within each GT.

To assess the consistency of the response across various subgroups, the SVR₁₂ and SVR₂₄ rates and associated 95% CIs will be estimated within each category of the following baseline factors as classification variables:

- Presence or absence of baseline RAVs to any of the 2 classes of drugs
- Gender (female, male)
- Age (≥ 65 , < 65)
- Race (White, Black or African American, Asian, Other)
- Ethnicity (Hispanic or Latino, not Hispanic or Latino)
- IL28B GT (CC versus non-CC GT)
- HCV RNA at baseline, $\leq 800,000$ IU/mL versus $> 800,000$ IU/mL; ≤ 2 million IU/mL versus > 2 million IU/mL; ≤ 10 million IU/mL versus > 10 million IU/mL
- Stage of fibrosis (non-cirrhotic [F0-F3], cirrhotic [F4])
- HIV co-infection status (HCV/HIV co-infected, HCV mono-infected)
- Treatment-experienced and treatment-naïve
- For GT1 subjects: (GT1a vs. GT1b)
- Geographical Region (US, Canada, European Union, Latin America, Asia Pacific, Middle East – note that regions may be collapsed depending on actual enrollment in the trial)

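### The APRI formula printed in inclusion criterion 4 does not fit the APRI cut-offs of ≤1 and >2 in the same criterion, so the FibroTest-plus-APRI staging route does not work as written

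*Combined protocol and SAP*

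**What the plan says.** Criterion 4 in Section 5.1.2 allows three ways to stage liver disease: biopsy, Fibroscan, or FibroTest combined with APRI (route iii). For absence of cirrhosis, route 4a(iii) needs FibroTest ≤0.48 together with "an aspartate aminotransferase (AST) to platelet ratio index (APRI) of ≤ 1". For cirrhosis, route 4b(iii) needs FibroTest >0.75 together with APRI >2. The index is then defined as "APRI formula: $AST \div lab\ ULN\ for\ AST \times 100 \div (platelet\ count \div 100" (bracket closed in the original), with no platelet unit. Next comes "APRI calculation to be provided by the testing laboratory", and a note adds: "In the absence of a definitive diagnosis of presence or absence of cirrhosis by the above criteria, a liver biopsy or Fibroscan[®] is required".

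Section 7.1.2.7 explains that the study chose a stricter version of a published algorithm, in which "both the APRI and FibroTest[®] need to be consistent with no cirrhosis". The platelet unit used elsewhere in the protocol is 10³/µL, in Table 6 (Section 5.1.3). That table excludes platelets below 50 × 10³/µL and AST above 10 × ULN.

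**The concern.** The expression multiplies by 100 and also divides the platelet count by 100, so a factor of 100 enters twice. The result is on a scale where cut-offs of 1 and 2 cannot both do their job. If the line is followed, the intended agreement between APRI and FibroTest is lost in one route and the other route is unusable.

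Stage matters in three places:

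- The Child-Turcotte-Pugh and liver-imaging exclusions (criteria 3 and 7 of Section 5.1.3) apply only to cirrhotic subjects.
- Section 2.1 sets a target of 25% to 30% cirrhotic subjects in each of GT1 to GT4. Section 4.2.2 counts the limit on cirrhotic subjects among the safeguards against virologic failure.
- Section 8.10 reports SVR12 and SVR24 by fibrosis stage within each genotype.

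**Working it through.** The documents give no worked APRI value to reproduce, so the check evaluates the printed formula over the range that Table 6 admits.

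**Inputs.** Let r = AST/ULN and P = platelet count. Printed formula (Section 5.1.2): r × 100 ÷ (P/100) = 10,000 r/P. Cut-offs (Section 5.1.2): ≤1 and >2. Eligible range (Table 6): r ≤10 and P ≥50 × 10³/µL. Assumed outer limits for the remaining corners: r ≥0.1 and P ≤450 × 10³/µL.

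**Platelets in 10³/µL.**
- At r = 1, P = 250: 10,000 × 1/250 = 40.
- APRI ≤1 needs r ≤ P/10,000, which is 0.025 at P = 250 and 0.045 at P = 450.
- APRI >2 needs r > P/5,000, which is 0.05 at P = 250 and 0.09 at P = 450.
- Range: 10,000 × 0.1/450 = 2.2 to 10,000 × 10/50 = 2,000.

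The ≤1 test cannot be met in practice and the >2 test is effectively always met.

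**Platelets per µL.**
- Maximum: 10,000 × 10/50,000 = 2.0 exactly, so >2 cannot occur in an eligible subject.
- APRI ≤1 fails only when r > P/10,000: r above 5 at P = 50,000, above 7.5 at 75,000, and above 10 (already excluded) at 100,000. The failing region is a corner with AST above 5 × ULN and platelets below 100,000/µL. On a uniform grid over the range above, 97% of points satisfy ≤1. That is a share of the grid, not of patients.

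**Other readings.** Cells per litre: maximum 10,000 × 10/(50 × 10⁹) = 0.000002. Units of 10⁴/µL: minimum 10,000 × 0.1/45 = 22. Multiplying the ULN by 100 instead gives r/P, with maximum 10/50 = 0.2 in 10³/µL and less per µL. In each case one cut-off is always met and the other never.

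**One factor of 100, platelets in 10³/µL.** Here APRI = 100 r/P, running from 100 × 0.1/450 = 0.02 to 100 × 10/50 = 20. The printed formula equals 100 times this value if P is entered in 10³/µL, and one tenth of it if P is entered per µL. The printed cut-offs therefore translate as follows:

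| | ≤1 as printed means single-factor APRI | >2 as printed means single-factor APRI |
|---|---|---|
| P in 10³/µL | ≤0.01 | >0.02 |
| P per µL | ≤10 | >20 (above the eligible maximum) |

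For example, r = 2 with platelets of 100 × 10³/µL gives 2.0 with one factor, and 200 or 0.2 as printed.

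**Who could be staged differently.** Taking the single-factor form as reference, in 10³/µL these are subjects with FibroTest >0.75 and single-factor APRI of 2 or less, who would pass as cirrhotic. Per µL they are subjects with FibroTest ≤0.48 and single-factor APRI above 1 and up to 10, who would pass as non-cirrhotic.

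**The case against.** The best defence is that sites are not asked to use the printed line. The laboratory supplies APRI, and Table 12 lists it as a screening laboratory item. Table 12's permission for local testing is attached to FibroTest, so it does not show that anyone calculated APRI locally. The laboratory may well have programmed something else. This limits the likely harm, but it does not repair the criterion: the printed line is the only APRI formula in the documents, and a laboratory that used another one departed from it without a record here.

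Second, a closed route does not itself misstage anyone. The note in criterion 4 sends subjects without a definitive result to biopsy or Fibroscan, and biopsy overrides the other methods. The cost is an extra procedure. This stands.

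Third, a reader might infer that route (iii) cannot tell the two groups apart at all. The documents do not support that, because the FibroTest limits of ≤0.48 and >0.75 apply whatever APRI does. Only subjects with discordant tests are exposed, and the documents give no count of them.

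Fourth, the documents contain no second APRI formula, so the single-factor version is shown to be workable, not proven to be the intended one. A misprint is possible: with counts per µL, a divisor of 1,000 in place of 100 gives the same values as the single-factor form. This stands, and it is why the remedy begins with reconciliation.

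**Conclusion.** The formula is wrong as written: under no platelet unit tried does it work with both of its own cut-offs. This follows from criterion 4 and Table 6 alone. Two qualifications apply. In 10³/µL, unreachable means that AST would have to be a few percent of the ULN, which is a practical impossibility and not an algebraic one. Per µL, the cap at 2.0 depends on the Table 6 limits, and the ≤1 test keeps a little force in the corner described.

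The consequence is confined to subjects staged by route (iii). It can reach the cirrhotic-only exclusions, the 25% to 30% target and the fibrosis subgroup. A reader might go further and infer that subjects were misstaged or that the main efficacy result is unsafe. The documents support neither: they do not show which formula the laboratory ran, and the primary analysis estimates SVR12 by genotype in the FAS (Section 8.6.1, Table 15) without using cirrhosis stage. The line needs correcting, but it is not a must-fix item for the primary analysis.

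**What to change.** 1. Check the line against the signed protocol. Then reconcile formula, platelet unit and cut-offs in criterion 4 with the testing laboratory, and print the unit. The candidate (AST/ULN) × 100 ÷ platelets in 10³/µL makes both cut-offs reachable.
2. Have the laboratory confirm in writing the formula and unit it programmed.
3. If it used the printed formula, re-derive APRI from the screening AST and platelet values for every subject staged by route (iii). Report how many change or lose their stage, and use the corrected stage in the Section 8.10 subgroup.
4. In the same edit, correct the sentence in Section 7.1.2.7 that lists the FibroTest and APRI cut-offs in the reverse of the order used in criterion 4.

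The cost is a one-line correction, a laboratory query and, if needed, a recalculation from data already held. No new sample is needed for the recalculation.
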